#### WM TASKS:

Two WM tasks will be performed a Delayed Response Alphabetization task (DRAT, Aim 1a, 1b, 1c) involving both maintenance and manipulation of information and a Delayed Response Maintenance Task (DRMT, Aim 1c) that only involved maintenance. Our implementation of the WM task for MRI consists of up to 10 runs of approximately 10-minute long letter-presenting blocks. Each trial begins with the presentation of a fixation cross during 5 seconds followed by the presentation of up to 9 uppercase letters arranged in a line. In the case where fewer letters are presented, all other positions are filled with asterisks. Stimuli are presented for up to three seconds before the screen is cleared. After a retention interval of 5 seconds, a probe stimulus is presented in the center of the screen for four seconds. The probe consists of the combination of a letter and a number, and which subjects are asked to answer. During this period subjects must press one of three keys indicating whether the number matches the position of the letter in the reorganized alphabetical order for the DRAT; or the serial position of the letter for the DRMT (Valid trials); or if the number does not match the letter position (Invalid trials); or if the letter did not belong to the array of letters (New, Aim 1a and 1b). Feedback is provided, at the end of each block as the overall accuracy. Tasks are performed with 1 (Hard, Aim 1c first cohort), 2 (Easy and Hard, Aim 1b and Aim 1c second cohort), or 3 (Easy, Medium, and Hard: Aim 1a) difficulty levels, defined as the number of letters presented on the screen and individually for each subject according to their performance during the screening visit. In rTMS sessions, the WM tasks will be run while stimulation is applied over the DLPFC (Aim 1a, Aim 1c) or the PC (Aim 1b, Aim 1c) either before the encoding (Aim 1a, Aim 1c) or during the delay period (Aim 1b, Aim 1c). Each block of trials will take about 10 minutes. To clarify all these conditions please refer to Figure 1 below.

	Group	Dosing	Timing	Site	Task	Difficulty	
Aim 1a	YA	100%rMT	Before the encoding	Frontal	DRAT	Easy	n= 29YA + 18 OA (6conditions/subj)
	OA	100%Eref 80%Eref	During the delay	Parietal	DRMT	Medium Hard	
Aim 1b	YA	100%rMT	Before the encoding	Frontal	DRAT	Easy	n= 15OA (4conditions/subj)
	OA	100%Eref 80%Eref	During the delay	Parietal	DRMT	Medium Hard	
Aim 1c Cohort 1	YA	100%rMT	Before the encoding	Frontal	DRAT	Easy	n= 15YA (4conditions/subj)
	OA	100%Eref 80%Eref	During the delay	Parietal	DRMT	Medium Hard	
Aim 1c Cohort 2	YA	100%rMT	Before the encoding	Frontal	DRAT	Easy	n= 14YA (8conditions/subj)
	OA	100%Eref 80%Eref	During the delay	Parietal	DRMT	Medium Hard	

**Figure 1:** Condition used for each sub-aims of the study, the highlighted cells represent the conditions used for each subaims.

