Aim 1a: rTMS applied over the DLPFC either before the encoding or during the delay period of the Delayed Response Alphabetization Task (DRAT, a working memory task in which participants were asked to maintain and reorganize in alphabetical order an array of letter) will be performed by young and older healthy adults with three difficulty levels, during 4 rTMS visits. Since it is expected that Valid (trials in which the number matches the position of the letter in the reorganized alphabetical order) and Invalid (trials in which the number does not match the position of the letter) trials will lead to strong differences in accuracy, two ANOVAs will be performed separately on each trial condition, for reaction time and accuracy. The two ANOVAs will be conducted with Group (Younger or Older adults), as the between-subject factor; and Visit (Visit 3, Visit 4, Visit 5 and Visit 6), Difficulty (Easy, Medium, and Hard), Stimulation Timing (Pre and Post) and Stimulation Type (Active and Sham) as the within-subject factor. If no difference are found between the two groups, they will be collapsed and the ANOVA will be performed on the larger sample.

Aim 1b: rTMS applied over the PC during the delay period of the DRAT performed with two difficulty levels in older adults, comparing the effect of two stimulation intensities defined with electric field modeling (E-field). A repeated measure ANOVA will be performed with Task Condition (Valid and Invalid), Stimulation Type (Active and Sham), Stimulation Amplitude (80% and 100% Eref), and Task Difficulty (Easy and Hard).

Aim 1c: rTMS applied over the DLPFC and the PC in younger adults performing the DRAT and the Delayed Response Maintenance Task (DRMT, an additional WM task added to the design and involving only the maintenance of the array of letter). rTMS will be applied before the encoding period of the WM tasks, performed with either one difficulty level (Hard) or two difficulty levels (Easy and Hard) in younger adults. A repeated ANOVA will be conducted with Task Condition (Valid and Invalid), Difficulty levels (only for subjects who performed the task with Easy and Hard difficulty levels), WM task (DRAT and DRMT), Stimulation Site (DLPFC and PC), and Stimulation Type (Active and Sham).

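### Aims 1a and 1b use a three-key task, but the planned TMS analyses cover only Valid and Invalid trials, so a drift away from the New key under active rTMS could raise both analysed accuracies with memory unchanged

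*Protocol*

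**What the plan says.** **Task.** Under WM TASKS, the protocol describes the probe response: "During this period subjects must press one of three keys indicating whether the number matches the position of the letter" (Valid), does not match it (Invalid), "or if the letter did not belong to the array of letters (New, Aim 1a and 1b"). New is therefore a response option in Aims 1a and 1b, and not in Aim 1c.

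**Analysis, Aim 1a.** The SAP (TMS data) states that "two ANOVAs will be performed separately on each trial condition, for reaction time and accuracy". The reason given for separating the trial types is that Valid and Invalid "trials will lead to strong differences in accuracy". New is not mentioned.

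**Analysis, Aim 1b.** "A repeated measure ANOVA will be performed with Task Condition (Valid and Invalid), Stimulation Type (Active and Sham"), with Stimulation Amplitude and Task Difficulty as further factors. Task Condition has two levels, and no dependent variable is named.

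**Elsewhere.** New trials do not appear in the SAP as an outcome, a factor level, catch trials or a stated exclusion. No sensitivity index, bias index or analysis of which wrong key was pressed is defined. The only pooled accuracy in either document is shown to the subject: "Feedback is provided, at the end of each block as the overall accuracy".

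**The concern.** Percent correct within one trial type reflects two things: whether the subject knows the answer, and how readily the subject presses that key when unsure. The study hypothesis is that active rTMS improves working-memory performance over sham. With three keys, a subject who becomes less inclined to answer New must press the other two more often. That raises accuracy on both analysed trial types, which is the pattern that would be read as enhancement.

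Agreement between Valid and Invalid would normally reassure a reader that an effect is not a response shift. It does not reassure here, because this shift moves both in the same direction. The loss appears on New trials, which no planned TMS analysis examines.

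**Working it through.** The documents state no accuracy level, trial count, trial mix or effect size, so there is no planned figure to reproduce. The calculation below is an illustration with stated assumptions.

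**Inputs from the documents**
- Three keys in Aims 1a and 1b (Protocol, WM TASKS).
- Aim 1a sample "n= 29YA + 18 OA (6conditions/subj"), so 29 + 18 = 47. Aim 1b sample "n= 15OA (4conditions/subj"), so 15 (Protocol, Figure 1).

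**Assumed model.** On each trial the subject knows the answer with probability m, the same under active and sham, and otherwise guesses key k with preference g_k. Then

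accuracy on type k = m + (1 − m) × g_k

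and the change from sham is (1 − m) × (change in g_k). Under sham, each g is 1/3.

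**Step 1: drift away from New.** g for New falls from 0.333 to 0.20, and g for Valid and for Invalid each rise from 0.333 to 0.40. The changes are (1 − m) × 0.067 for Valid and Invalid, and (1 − m) × (−0.133) for New.

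| m | Valid | Invalid | New |
|---|---|---|---|
| 0.4 | +4.0 points | +4.0 | −8.0 |
| 0.6 | +2.7 | +2.7 | −5.3 |
| 0.8 | +1.3 | +1.3 | −2.7 |

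At m = 0.6, Valid and Invalid accuracy go from 73.3% to 76.0%, and New accuracy from 73.3% to 68.0%.

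**Step 2: does d' respond?** Take d' = z(rate of answering Valid on Valid trials) − z(rate of answering Valid on Invalid trials), at m = 0.6.
- Sham: rates 0.6 + 0.4/3 = 0.733 and 0.4/3 = 0.133, so d' = 0.623 + 1.111 = 1.73.
- Active: rates 0.6 + 0.4 × 0.40 = 0.760 and 0.4 × 0.40 = 0.160, so d' = 0.706 + 0.994 = 1.70.

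Percent correct rises on both types while d' falls slightly, so d' gives no false gain.

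**Step 3: shift from Invalid to Valid by 0.10, for comparison.** At m = 0.6, Valid changes by 0.4 × 0.10 = +4.0 points, Invalid by −4.0, and their mean by 0. In Aim 1a the two ANOVAs would move in opposite directions. In Aim 1b the shift would appear as a Stimulation Type × Task Condition interaction with no main effect. The planned analysis can reveal this shift.

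**Step 4: how often the Step 1 drift would be declared a benefit.** Simulated paired active-minus-sham t-tests (4,000 runs, two-sided 0.05, counting only rejections that favour active; between-subject SD of m 0.10; equal numbers of each trial type). With m = 0.6 and 80 trials per type per arm:
- n = 47: about 75% for each of Valid and Invalid.
- n = 15: about 29% for each.

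With m from 0.4 to 0.8 and 40 to 160 trials, the rates run from 22% to above 99% at n = 47 and from 9% to 77% at n = 15. The nominal rate is 2.5%. Every simulated subject has the same shift, and a t-test stands in for the planned ANOVAs, so these rates show only that a shift of a few points need not be lost in noise.

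**Step 5: is mean accuracy a safe alternative?** In the know-or-guess model the mean over three equally frequent types does not move. That result depends on the model. In an equal-variance signal-detection model of the Valid/Invalid decision, with d' = 1.5 and a criterion starting 0.4 SD against Valid, a 0.2 SD shift towards Valid moves the mean from (0.637 + 0.875)/2 = 0.756 to (0.709 + 0.829)/2 = 0.769. That is a spurious gain of 1.3 points with sensitivity fixed.

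**The case against.** The strongest reply is that the plan already has a check on response bias: it analyses both Valid and Invalid trials. This stands for one kind of shift. A reader might infer that any change in key preference could pass as better memory, including a greater readiness to press Valid. The documents do not support that, because such a shift lowers Invalid accuracy, which is tested (Step 3). A drift towards New would lower both accuracies and look like harm. Only a drift away from New both mimics benefit on the two analysed types and escapes them.

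A second reply is that the size is assumed throughout. This also stands. Nothing in the documents indicates that rTMS alters key preference, and active and sham are compared within subject, so a stable personal preference cancels. The point concerns only a preference that differs between active and sham.

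Third, it would go too far to say that New trials are never used or that accuracy is the only outcome. Aim 1a also analyses reaction time. Aim 1b names no outcome, so percent correct is an inference there. The SAP's fMRI section predicts WM performance without restricting trial type, and the protocol does not say whether New trials enter the block feedback or the individual difficulty setting. The omission is established for the planned TMS ANOVAs only.

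Finally, separating Valid from Invalid has a stated reason, and replacing that analysis with a single index would be a debatable trade. This is a reason to add to the plan and leave what is there intact.

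**Conclusion.** The point holds in a limited form. In Aims 1a and 1b one of three response categories is absent from the planned TMS analyses, without explanation, and no bias-resistant measure is defined. A drift away from New under active rTMS would then appear as a consistent accuracy gain that no planned TMS test could distinguish from better memory.

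Under the assumed model with 60% of answers known, the false gain is 2.7 points on each analysed type (1.3 to 4.0 points for 80% down to 40% known), against a 5.3-point loss on New. These figures rest on the know-or-guess form, the chosen shift from 0.333 to 0.20, and equal guessing under sham. The rejection rates rest further on assumed trial counts and an identical shift in every subject.

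It does not follow that the trial's accuracy results are biased, or that a Valid-Invalid shift would go unseen. Because the remedy uses responses that the task already collects, the change is worth making without evidence that the drift occurs.

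**What to change.** 1. Keep the planned Valid and Invalid analyses.
2. State the number and share of New trials. In Aim 1a, run the same ANOVA on New trials. In Aim 1b, add New as a further level of Task Condition or analyse it in a parallel ANOVA, and name the dependent variable.
3. Pre-specify Valid-versus-Invalid d' as an added accuracy outcome in both aims: the rate of answering Valid on Valid trials against the rate on Invalid trials, with a stated correction for empty cells.
4. Pre-specify the reading rule: an accuracy gain under active rTMS counts as better working memory only if d' also improves and New accuracy shows no offsetting fall. Both conditions matter, since d' makes no use of New trials.
5. Do not present mean accuracy over trial types as free of key preference (Step 5).

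The cost is SAP wording and rescoring of responses, with no new procedure or visit. The downsides are one more trial type to test and a small correction to d' in error-free cells. If the sponsor has a reason to leave New trials out, the SAP should state it.

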#### MOTOR THRESHOLD DETERMINATION:

All rTMS procedures will occur in the Noninvasive Neuromodulatory Neuroscience (N3) Lab in rooms 54211 and 54212 in the Department of Psychiatry and Behavioral Sciences, Duke Clinic South. Motor threshold (MT) is defined as the minimum magnetic flux needed to elicit a threshold EMG response in a target muscle in 5 out of 10 trials. MT is the standard in the field for determining the intensity of rTMS for each individual to reduce seizure risk. The motor evoked potentials (MEP) for the contralateral first dorsal interosseous (FDI) will be measured with EMG. The scalp region producing the largest amplitude MEP will be identified. At that scalp location, the lowest TMS intensity able to elicit 5 MEP's of  $\geq 50\mu\text{V}$  in peak-to-peak amplitude in 10 trials at this site will be determined, using a descending method-of-limits procedure initiated by the MUSC PEST program.

MT will be determined for one or both hemispheres with the muscle at rest (verified by baseline EMG). Individual MT will be used to determine the intensity of stimulation for each individual, as recommended by safety guidelines.

#### **MRI/fMRI PROCEDURE:**

At BIAC, after obtaining a structural MRI and DTI and resting-state fMRI scans, fMRI data will be recorded from subjects while they perform the WM task. BOLD images will be acquired with a 3.0T GE MR Scanner. Stimuli will be back-projected onto a screen located at the head of the MRI bed using an LCD projector. Subjects will view the screen via a mirror system located in the head coil. Task onset will be electronically synchronized with the MRI acquisition computer. Task administration and collection of RT and accuracy data will be computer controlled. The scanning session will take about 1.5 hr.

Studies will be using a GE Premier Performance 3T MRI scanner, which is an improved version of GE's FDA-approved Premier system, but with better capabilities for high-resolution imaging. All operational parameters on this improved system will be within FDA guidelines to meet the same minimal risk device criteria and ensure safety of human subjects. As such, an Investigational Device Exemption (IDE) is not necessary. The research conducted under this protocol is not to evaluate the safety and efficacy of this device.

#### **APPLICATION OF RTMS DURING WM TASK PERFORMANCE:**

The subject will be seated comfortably in a chair, facing a computer screen positioned in front of the subject for visual stimulus presentation. Earplugs will be worn to protect hearing. The participant's head may be held steady by a frame with a chin rest and the rTMS coil holder frame. A figure eight magnetic coil will be placed on the scalp and held in place with a coil fixing system supplied by MagVenture. This will be paired with the BrainSight tracking system which provides precise fMRI-guided rTMS coil placement for basic, translational, and clinical applications of rTMS. The BrainSight program enables the coil to be placed at precise cortical targets (chosen from the subject's fMRI activations from the WM task from the MRI session) on the individual's 3-dimensionally rendered brain MRI with less than one millimeter error, and enables the research team to dynamically move the coil to account for slight head movements while the subject performs the task. Five-second trains of 5 Hz rTMS will be administered at up to 130% of the individual's MT with the stimulating coil tangential to the scalp. Sham rTMS will be administered with a sham coil equipped with shielding to block magnetic field output but retain the auditory and some of the tactile aspects of active stimulation. rTMS administration will be controlled by an external computer and will be time-locked relative to stimulus presentation. A brief rTMS side effect rating scale and visual analog mood ratings will be administered before and after each rTMS block. There will be up to 12 blocks of trials per session, and each session will take about 2 hrs. Subjects' side-effects will be monitored closely. As indicated in the procedures section, side effects are assessed in a charted, structured interview both prior to and after the rTMS session. Subjects are instructed during the consent process and during the rTMS sessions about all known side effects. They are further instructed during consenting and additionally at the conclusion of the rTMS session to contact the principal investigator or study physician with any questions or concerns (including those that may arise after the experimental session has ended).

**Imaging acquisition and preprocessing.** Three forms of structural images will be acquired: **1) full-brain high-resolution T1-weighted structural images** (inversion recovery prepared 3D SPGR) with full coverage of the head and neck, (TR = 500ms; TE = 20ms; FoV = 24cm^2; image matrix = 256x256; voxel size = 0.94 x 0.94 x 1mm), and **2) echo-planar (EPI) sensitivity encoding (SENSE) DWI images** with the same orientation (TR = 2000 ms; FoV = 24 cm^2; image matrix = 128; voxel size 0.94 x 0.94 x 1 mm; b-value = 1000 s/mm^2; 1 repetition; 36 diffusion-sensitizing directions). In addition, two forms of functional images will be collected: **1) for resting state EPI** functional imaging data, which will be used to estimate RSFA, we will acquire 24 slices parallel to the AC-PC plane using a BOLD-sensitive gradient-echo sequence with EPI k-space sampling, at TR of 2s (TE: 35ms; FOV: 25.6cm; voxel size: 63mm), and **2) event-related EPI**, which uses the same scan parameters and will measure the global reactivity to our Working Memory Task.

**TMS methods.** Coil targeting will be achieved using frameless stereotaxy (BrainSight: Rogue Research, Montreal). TMS is applied with a figure 8 coil based on 100% resting motor threshold (rMT), though TMS intensity will also be informed by E-field modeling (described below). TMS will be delivered consecutively over the individualized target region, based on the cortical site with the highest computed controllability (Network target) or parametric activity (Activity target), using a MagVenture stimulator. Neuronavigation (BrainSight, Rogue Research, Canada) and a robot (SmartMove, ANT, Netherlands) will be used to optimize the targeting. Brain atrophy could also reduce TMS effectiveness because it increases the distance between scalp and the cortex but this potential confound is addressed by adjusting TMS intensity using the E-field computation. In visits 3 to 6, participants will perform the Working Memory Task while active or electrical sham stimulation is delivered using an A/P Cool-B65 coil (MagVenture, Denmark). In a stimulation trial, twenty-five pulses of 5Hz

rTMS will be delivered at 100% of the effective E-field. Sham rTMS will be administered with a sham coil equipped with shielding to block magnetic field output but retain the auditory and some of the tactile aspects of active stimulation. This method reproduces the somatosensory sensations as the magnetic field stimulates scalp muscles, and produces the same acoustic artifact than the active stimulation, without inducing current in the cortex.

**E-field Modeling.** In order to determine the *intensity* of network-based targeting, we will use electric field (E-field) modeling. The BSEL lab has extensive experience with the creation of anatomically realistic E-field models of transcranial electric and magnetic stimulation in humans, which have been applied to healthy OA populations in ongoing NIH-funded projects by Co-I's [name] and [name] (U01-AG050618), using SimNIBS software. A detailed model of the TMS coil is combined with a detailed head model. Isotropic tissue conductivities are assigned to the various tissue compartments. Critically, this method will also include anisotropic conductivity in the white matter based on the DWI data. We will carry out E-field simulations over a range of coil orientations and tilts to predict maximal activation of the FPN. The target node (i.e., the node with the highest controllability, identified above) will be used as the center of a  $3\times 3$  grid for positioning the coil in simulations of the E-field corresponding to these 9 coil positions and 6 orientations (54 combinations). The simulation E-field maps will be extracted and correlated, voxel-to-voxel, with the fMRI activation and the simulation that yields the highest correlation is selected as the target coil position and orientation.

Using TMS to Increase Executive Function in Older Adults

NCT02767323

Statistical Plan

Date of Approval:

01/19/2021

Data Analysis & Statistical Considerations

fMRI data:

All image pre-processing will be implemented using the FSL program (<https://fsl.fmrib.ox.ac.uk/fsl/fslwiki>). Event-related fMRI data will be extracted by time-series modeling using rectangular time windows for the memory encoding and probe phases of the task, one modeling a brief (400 ms) neural response at the beginning of the task phase, and another modeling a neural response lasting for the entire 3000 ms phase. A single rectangular function of 7000 ms will be used for the retention phase. Group data will then be analyzed using ordinal trends model (OrT: a newly-developed multivariate covariance analysis). Any fMRI network related to performance in the WM task from previous fMRI research using the WM task in young and elderly subjects will be prospectively applied to the fMRI data of the subjects. Specifically, the imaging data from the pre- and post-MRI sessions will be log transformed and subtracted from each other at each site in each subject. The global mean across sites will be subtracted from each log-transformed regional value, producing regional values normalized to each subject's global mean activity. In a second normalization, the mean for each site across subjects will be subtracted from each regional value. The result of these two normalizations is a subject x region matrix with the mean activity within and across subjects removed. This will be cross-correlated with the patterns previously found in order to quantify pattern expression for individual subjects in the present group. These individual subject pattern expressions will be entered into regressions predicting WM performance in order to verify that the patterns predict performance in new group. In addition, pattern expression will be used to predict rTMS effects on WM performance (for example, differences in RT with active and sham rTMS).

TMS data:

Aim 1a: rTMS applied over the DLPFC either before the encoding or during the delay period of the Delayed Response Alphabetization Task (DRAT, a working memory task in which participants were asked to maintain and reorganize in alphabetical order an array of letter) will be performed by young and older healthy adults with three difficulty levels, during 4 rTMS visits. Since it is expected that Valid (trials in which the number matches the position of the letter in the reorganized alphabetical order) and Invalid (trials in which the number does not match the position of the letter) trials will lead to strong differences in accuracy, two ANOVAs will be performed separately on each trial condition, for reaction time and accuracy. The two ANOVAs will be conducted with Group (Younger or Older adults), as the between-subject factor; and Visit (Visit 3, Visit 4, Visit 5 and Visit 6), Difficulty (Easy, Medium, and Hard), Stimulation Timing (Pre and Post) and Stimulation Type (Active and Sham) as the within-subject factor. If no difference are found between the two groups, they will be collapsed and the ANOVA will be performed on the larger sample.

Aim 1b: rTMS applied over the PC during the delay period of the DRAT performed with two difficulty levels in older adults, comparing the effect of two stimulation intensities defined with electric field modeling (E-field). A repeated measure ANOVA will be performed with Task Condition (Valid and Invalid), Stimulation Type (Active and Sham), Stimulation Amplitude (80% and 100% Eref), and Task Difficulty (Easy and Hard).

Aim 1c: rTMS applied over the DLPFC and the PC in younger adults performing the DRAT and the Delayed Response Maintenance Task (DRMT, an additional WM task added to the design and involving only the maintenance of the array of letter). rTMS will be applied before the encoding period of the WM tasks, performed with either one difficulty level (Hard) or two difficulty levels (Easy and Hard) in younger adults. A repeated ANOVA will be conducted with Task Condition (Valid and Invalid), Difficulty levels (only for subjects who performed the task with Easy and Hard difficulty levels), WM task (DRAT and DRMT), Stimulation Site (DLPFC and PC), and Stimulation Type (Active and Sham).

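### The SAP models a 7000 ms retention phase and a 3000 ms probe, but the protocol's MRI task has a 5 s retention and a 4 s probe

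*SAP*

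**What the plan says.** The protocol, under WM TASKS, introduces the timings as those of the scanner version: "Our implementation of the WM task for MRI consists of up to 10 runs of approximately 10-minute long letter-presenting blocks". It then sets out the trial:

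- Fixation: "Each trial begins with the presentation of a fixation cross during 5 seconds".
- Letters: "Stimuli are presented for up to three seconds before the screen is cleared".
- Retention and probe: "After a retention interval of 5 seconds, a probe stimulus is presented in the center of the screen for four seconds".

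The SAP, under fMRI data, describes the first-level model for this task. It uses "rectangular time windows for the memory encoding and probe phases of the task". Each of these two phases gets one window for a brief 400 ms response and "another modeling a neural response lasting for the entire 3000 ms phase". For the delay it says: "A single rectangular function of 7000 ms will be used for the retention phase". It gives no onset for any window.

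Later in the same section, pattern expression is derived from the imaging data. "These individual subject pattern expressions will be entered into regressions predicting WM performance", and pattern expression is also to be used to predict rTMS effects on performance.

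**The concern.** The two documents give different lengths for two of the three modelled phases of one task. Both are dated 01/19/2021, so an amendment does not explain the gap. The protocol timings are explicitly those of the MRI task, so a difference between scanner and rTMS sessions does not explain it either. Neither document mentions a second MRI version, a jittered delay or cohort-specific timing.

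In an event-related model the window lengths decide which signal is attributed to which phase. If the protocol timings were run, a retention window that is too long must overlap a neighbouring phase, and a probe window that is too short leaves part of the probe unmodelled. The phase estimates are then biased, and so is pattern expression if it is built from them. If 7 s and 3 s were run, the SAP is right and the protocol misdescribes the task. A reader cannot tell which.

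**Working it through.** **Durations side by side** (Protocol, WM TASKS; SAP, fMRI data)

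| Phase | Protocol | SAP window | Difference |
|---|---|---|---|
| Encoding | up to 3000 ms | 3000 ms | none at the maximum |
| Retention | 5000 ms | 7000 ms | +2000 ms; 7/5 = 1.40, so 40% longer |
| Probe | 4000 ms | 3000 ms | -1000 ms; 3/4 = 0.75, so 25% shorter |
| Total | 3 + 5 + 4 = 12 s | 3 + 7 + 3 = 13 s | +1 s |

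With the 5 s fixation the trial lasts 17 s on the protocol timings and 18 s on the SAP timings.

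**Overlap if the protocol timings were run.** Count from letter onset. Retention occupies 3 to 8 s and the probe 8 to 12 s. A 7 s window starting at letter offset covers 3 to 10 s, so it overlaps the probe by 10 - 8 = 2 s, half of it. A 3 s probe window from 8 s ends at 11 s, leaving 12 - 11 = 1 s unmodelled. If the 7 s window ends at probe onset instead, it covers 1 to 8 s and overlaps 2 s of encoding.

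**Illustrative noise-free fit.** From the documents: trial 5 + 3 + 5 + 4 = 17 s, runs of about 600 s (600/17 gives 35 trials), and TR 2 s (Protocol, Imaging acquisition and preprocessing). Assumed: fixed spacing and full 3 s letters. Three response shapes were tried: a double-gamma, a single gamma with mean 6 s and SD 3 s, and a double-gamma with a deeper undershoot. The signal is generated with the protocol durations and fitted by least squares with the SAP durations. Ranges cover the three shapes and small differences in run layout. True activity is listed as (encoding, retention, probe); the true value of every brief coefficient is 0.

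| Retention window; probe regressor start | True activity | With 400 ms windows | Without them |
|---|---|---|---|
| 3 to 10 s; 8 s | (0, 1, 0) | retention 1.00 to 1.03; sustained probe -0.44 to -0.47; brief probe -2.0 to -2.2 | retention 0.93; probe -0.61 to -0.65 |
| 1 to 8 s; 8 s | (0, 1, 0) | sustained encoding -0.88 to -0.89; sustained probe within 0.03 of 0 | encoding -0.61 to -0.65; probe within 0.03 of 0 |
| 3 to 10 s; 10 s (SAP windows end to end) | (0, 1, 0) | sustained probe +0.30 to +0.37; brief probe -5.2 to -5.5 | probe -0.35 to -0.42 |
| 3 to 10 s; 8 s | (1, 1, 1) | retention 0.95 to 1.08; sustained probe 0.95 to 1.18; brief probe -4.2 to -6.0 | not tabulated |
| Matched 5 s and 4 s | (0, 1, 0) | truth recovered | truth recovered |

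Omitting the constant term moves the first row's sustained-probe estimate to about -0.42 with the 400 ms windows and -0.57 to -0.58 without.

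In the first row the sustained and brief probe coefficients are both negative, so the fit shows a probe deactivation that is not there. The third row shows that the sign of the sustained term depends on the onsets, which the SAP does not give.

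**The case against.** The strongest objection is that little depends on this. The primary objective is working-memory performance under active versus sham rTMS, and the ANOVAs in the SAP's TMS data section do not use the fMRI model. The SAP does not say which regressor feeds pattern expression. It also differences log-transformed pre- and post-session data and removes subject and site means, which could cancel an error common to both sessions or to all subjects at a site. All of this stands. It limits the consequence but does not remove the discrepancy, and leakage that varies with activity need not cancel.

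A second objection is that the headline scenario is extreme. Even there the retention coefficient stays near 1 with the SAP's 400 ms windows, and with all three phases active the sustained estimates lie close to the truth. This is correct and is why the working shows those values. The error appears in the probe or encoding terms, and in the all-active case the brief probe term is still badly distorted.

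Third, a modelling window need not equal the phase it models, or timings might have differed between cohorts. The first reading is arguable for retention but not for the probe, where the SAP presents 3000 ms as the length of the whole phase. Nothing in either document supports the second.

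**Conclusion.** The concern holds. The mismatch is certain and can be read directly from the two texts: retention 7000 against 5000 ms, probe 3000 against 4000 ms. Any bias is conditional on the protocol timings having been run and the SAP windows having been used as written. Its size, sign and location depend on window onsets, response shape and activity profile, so the fitted values above illustrate the mechanism and do not size any planned result. If only the wording of one document is wrong and the regressors follow the task as run, no estimate is biased. The exposure is confined to the fMRI phase estimates and whatever is built on them. The behavioural ANOVAs are unaffected, and no error in rTMS targeting is claimed. It should be corrected because it concerns a pre-specified analysis setting and costs almost nothing to put right.

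**What to change.** 1. Confirm the scanner timings from the task program or its timing records. The documents do not mention these; their existence is assumed.
2. Set the onset and duration of every regressor to the timings actually run, and state both in the SAP for each window.
3. Correct whichever document is wrong. If the protocol timings hold, the SAP should give a 5000 ms retention regressor and a 4000 ms sustained probe regressor. If 7 s and 3 s were run, correct the task description under WM TASKS in the protocol.
4. As a clarification only, state that the encoding regressor equals the time the letters were shown, since the protocol gives three seconds as a maximum.
5. State which phase estimate, if any, enters pattern expression, so that a reader can see what depends on these settings.

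The cost is wording in one or both documents and, if the model was set up with the wrong windows, a change to the first-level settings and a refit. No new data are needed.
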